### Objectives

Primary objectives:

1. To evaluate the safety and tolerability of TNP-2092 Capsules in liver cirrhosis patients with hyperammonemia.
2. To evaluate the pharmacokinetic characteristics of TNP-2092 Capsules in liver cirrhosis patients with hyperammonemia.

Secondary objectives:

1. To evaluate the preliminary efficacy of TNP-2092 Capsules in liver cirrhosis patients with hyperammonemia.
2. To observe the effects of TNP-2092 Capsules on hepatic encephalopathy related clinical symptoms and signs, neuropsychological indicators, and quality of life in liver cirrhosis patients with hyperammonemia.

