### Study Design

The aim of this study is to evaluate the safety, tolerability, and pharmacokinetic characteristics of TNP-2092 Capsules in liver cirrhosis patients with hyperammonemia; and to preliminarily observe the effects of the study drug on blood ammonia and hepatic encephalopathy related clinical symptoms and signs, neuropsychological indicators, and quality of life in liver cirrhosis patients with hyperammonemia.

A total of 3 dose groups will be set up, i.e., 100 mg BID, 300 mg BID and 600 mg BID groups. Drugs will be orally administered 30 min after breakfast and dinner for 14 consecutive days, and last dose will be administered 30 min after breakfast on the morning of D15. Each dose group will include a study drug TNP-2092 capsule arm and a placebo control arm. Subjects will exit upon completion of the safety and tolerability evaluation on D17.

Twelve liver cirrhosis patients with hyperammonemia are planned to be enrolled in each dose group. The 12 patients will be assigned in a ratio of 2:1 to the TNP-2092 capsule arm and the placebo arm, with 8 patients receiving TNP-2092 Capsules and 4 receiving placebo.

In each dose group, a sentinel-based sequential enrollment design will be applied, and the 12 patients will be sequentially enrolled into two subgroups which will consist of 3 and 9 patients

respectively. If the drug is evaluated as tolerable in the safety and tolerability assessment on D2, D4 and D7 of treatment in the first subgroup, enrollment for the next subgroup may start.

Enrollment for the second dose group may start only after the previous dose group has fully completed the treatment period and passed the safety and tolerability evaluation.

During the study, safety and tolerability will be observed and evaluated in subjects at scheduled time points in the protocol. PK blood samples will be collected from subjects at scheduled time points in the protocol for pharmacokinetic analysis.

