**Efficacy analysis:**

All efficacy endpoints will be descriptively summarized. Changes at each post-baseline visit from baseline will be calculated for all endpoints except asterixis.

For fasting blood ammonia concentration, if data follow a normal distribution, single-group t-test will be used to determine, by treatment group, whether the change from baseline at each post-baseline time point is 0; and analysis of covariance will be performed for differences between treatment groups and between each treatment group and the control group in changes from baseline at each post-baseline time point. If data do not follow a normal distribution, Wilcoxon signed rank test and Wilcoxon rank sum test will be used. The areas under the blood ammonia concentration-time curve will be calculated, and t-test or Wilcoxon rank sum test will be used for inter-group comparison. Normal fasting venous blood ammonia concentrations across all post-baseline visits in each dose group and the placebo group will be counted, and their percentages in all measurements will be calculated; Logistic regression will be used to compare the difference in the percentage of normal blood ammonia concentrations between each dose group and the placebo group.

With regard to whether asterixis is elicited, baseline, D7 and D15 results will be compared by treatment group using paired chi-square test; Logistic regression (with baseline and group as

independent variables) or non-parametric methods will be used for inter-group comparison of D7 and D15 results.

For NCT-A and DST results, t-test or Wilcoxon signed rank test will be used to determine whether the change from baseline in each treatment group is 0 on D7 or D15. Inter-group t-test or Wilcoxon rank sum test will be used to determine whether changes on D7 and D5 are different between treatment groups and between each treatment group and the control group.

NCT-A and DST results will be analyzed using age-corrected scaled scores.

For the quality of life scale for patients with mild hepatic encephalopathy, the total score of the 30 questions will be calculated for the subject, and paired t-test will be used to determine whether the change from baseline at each post-baseline visit is 0 within each group; and analysis of covariance (baseline as the covariate and group as the fixed factor) to determine whether changes from baseline at each post-baseline visit are different between the groups (including the placebo group).

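### The normal-ammonia comparison pools repeated values per patient in a logistic regression with no patient term, so its p-values are generally too small

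*Combined protocol and SAP*

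**What the plan says.** The rule is in the combined protocol and SAP, Statistical methods, Efficacy analysis. It first defines the count: "Normal fasting venous blood ammonia concentrations across all post-baseline visits in each dose group and the placebo group will be counted". It then gives the denominator and the test: "their percentages in all measurements will be calculated; Logistic regression will be used to compare the difference in the percentage" between each dose group and placebo. Numerator and denominator are both measurements, and no model terms are listed.

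The same section does list terms for its other logistic model, the one for asterixis: "Logistic regression (with baseline and group as" independent variables. That model has no patient term either.

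The remaining between-group ammonia analyses do not pool. Change from baseline is tested separately at each post-baseline time point ("analysis of covariance will be performed for differences between treatment groups and between each treatment group and the control group", with a rank sum test if the data are not normal). For the area under the ammonia curve, "t-test or Wilcoxon rank sum test will be used for inter-group comparison".

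The Study Design section sets three dose groups of 12, each "with 8 patients receiving TNP-2092 Capsules and 4 receiving placebo". The Objectives section makes efficacy secondary: "To evaluate the preliminary efficacy of TNP-2092 Capsules in liver cirrhosis patients with hyperammonemia".

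**The concern.** Treatment is assigned to patients, while this test counts measurements. Several ammonia values from one patient with cirrhosis are likely to resemble each other, so they carry less information than the same number of values from different patients. Ordinary logistic regression on the pooled values ignores this and gives standard errors that are too small.

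With 8 active patients per dose, a few who are persistently normal could then look like a drug effect. Normalisation of ammonia is easy to quote, and this result could disagree with the time-point and AUC comparisons for a purely statistical reason. The plan also leaves open whether baseline ammonia enters the model and whether placebo is pooled over the three dose groups.

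**Working it through.** **Inputs from the documents.** Three dose groups; 12 patients each at 2:1, so 8 active and 4 placebo. A dose group is compared with 3 × 4 = 12 placebo patients if placebo is pooled, and with 4 if not. The plan states no power, significance level or expected rate for this endpoint, so there is no figure of its own to reproduce.

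**Assumptions, not in the documents.** K = 2, 4 or 7 post-baseline ammonia values per patient; within-patient correlation (ICC) 0.2 to 0.5; 30% of values normal; two-sided 5% level.

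**Step 1: design effect.** The standard error is too small by the factor √(1 + (K − 1) × ICC), and the large-sample true size of a 5% test is 2 × [1 − Φ(1.96 / factor)].

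| K | Factor, ICC 0.2 | Factor, ICC 0.5 | Large-sample size |
|---|---|---|---|
| 2 | √1.2 = 1.10 | √1.5 = 1.22 | 7.4–11.0% |
| 4 | √1.6 = 1.26 | √2.5 = 1.58 | 12.1–21.5% |
| 7 | √2.2 = 1.48 | √4.0 = 2.00 | 18.6–32.7% |

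**Step 2: simulation at the actual sample sizes.** Beta-binomial patients, no drug effect, 20,000 trials per cell, pooled logistic regression with group only; separated data count as non-rejection for Wald. Rejection rates over ICC 0.2–0.5:

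| Patients | K | Likelihood ratio | Wald |
|---|---|---|---|
| 8 vs 12 | 2 | 7.9–12.0% | 5.3–8.1% |
| 8 vs 12 | 4 | 13.1–23.3% | 11.7–21.2% |
| 8 vs 12 | 7 | 18.9–33.8% | 18.4–33.1% |
| 8 vs 4 | 2 | 9.9–15.8% | 3.4–4.8% |
| 8 vs 4 | 4 | 13.2–24.5% | 9.6–16.6% |
| 8 vs 4 | 7 | 19.6–35.8% | 17.7–30.7% |

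With ICC = 0 the rates are 5.2–7.1% (likelihood ratio) and 2.4–5.0% (Wald), so most of the excess comes from clustering.

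**Step 3: sensitivity to the normal rate (K = 4, 8 vs 12, ICC 0.2–0.5).** At 50% normal: 12.6–22.6% (likelihood ratio), 12.3–22.1% (Wald). At 15% normal: 14.6–25.4% and 8.2–13.6%. At 15% normal with K = 2, the Wald test is not inflated (2.1–3.1%), while the likelihood-ratio test is (8.9–13.0%).

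**Step 4: a limiting example (ICC = 1, K = 4).** Suppose 4 of 8 active and 2 of 12 placebo patients are always normal and the rest never.
- Pooled, this is 16/32 vs 8/48. The log odds ratio is ln[(16 × 40)/(16 × 8)] = ln 5 = 1.609, with standard error √(1/16 + 1/16 + 1/8 + 1/40) = 0.524. So z = 3.07 and p = 0.002 (Wald); the likelihood-ratio p is 0.0015.
- By patient, it is 4/8 vs 2/12. The exact two-sided p is (4620 + 672 + 28 + 924)/38760 = 0.16.

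**Step 5: patient-level analysis under the null.** An exact Wilcoxon test on each patient's proportion of normal values (30% normal, ICC 0.2–0.5) rejects in 3.3–5.1% of trials at 8 vs 12 and 1.8–3.8% at 8 vs 4. A t-test on the same proportions stays at about 4–6% when K is 2 or more.

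**The case against.** The strongest reply is that the text is a synopsis that names methods briefly. Logistic regression does not exclude a clustered fit, and the ammonia ANCOVA lists no terms either, so the missing terms may only be brevity. That weakens any inference from the contrast with asterixis. It does not rescue the analysis: the measurement is explicitly the unit, nothing in the plan requires a patient term, and a programmer following the sentence would fit an ordinary model. If clustering were added later, the choice could be made with the data in view.

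The second reply is that the size is assumed, and this stands. All patients enter with ammonia above the upper limit of normal, so a low normal rate is plausible. At 15% normal and 8 vs 4, the Wald test rejects in only 1.1–1.6% of trials at K = 2 and 5.1–8.2% at K = 4, although the likelihood-ratio test remains inflated (8–13% and 15–27%). At an ICC of 0.05–0.1 (K = 4, 8 vs 12, 30% normal) inflation is modest: 6.9–9.2% (likelihood ratio) and 6.0–8.1% (Wald). The plan does not say which test would be used. The example in step 4 is an extreme and shows the mechanism, not a likely result.

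Third, little depends on this p-value, and the choice of Wilcoxon over a clustered model is partly preference. Both are fair: any prespecified method that respects the patient as the unit would remove the error.

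**Conclusion.** The concern holds. As written, the comparison treats repeated values from one patient as independent, and its p-values are generally too small. With four to seven values per patient, an ICC of 0.2–0.5 and 30% normal values, the true error rate of a nominal 5% test is roughly 10–36%, depending on the test and on placebo pooling. With two values per patient it ranges from no inflation (Wald, 8 vs 4) to about 16% (likelihood ratio, 8 vs 4). The direction rests only on positive within-patient correlation; the size rests on a visit count and an ICC that the documents do not give.

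The reach is narrow. No decision rule is tied to this test, and the primary safety and pharmacokinetic objectives and the other between-group ammonia comparisons are unaffected. It should be fixed so that this result is not quoted as support for efficacy on an invalid p-value.

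**What to change.** In the Efficacy analysis section, replace the pooled logistic regression as follows:

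- For each patient, compute the proportion of post-baseline fasting ammonia values that are normal. Compare each dose group with placebo by an exact Wilcoxon rank sum test on these proportions.
- State whether placebo is pooled across the three dose groups.
- Keep the pooled percentage of measurements as a descriptive figure without a p-value.
- If a model is wanted, make it a sensitivity analysis: a logistic model clustered on patient with a small-sample correction, stating whether baseline ammonia is included.

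The cost is a short change of SAP wording and a few lines of code, with no new data. P-values will usually, though not always, be less favourable. The exact test is conservative at 8 vs 4, so some power is lost if placebo is not pooled.

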### **Admission (Baseline) Evaluations**

Admission (baseline) will be occurred on D-1.

Baseline evaluations: Medical history, surgical history, clinical laboratory tests, physical examination, vital signs, 12-lead ECG, serum pregnancy test (females only), urine drug screen, alcohol breath test, fasting blood ammonia concentration, asterixis, Neuropsychological evaluation: Number connection test (NCT-A) and Digit symbol test (DST), Quality of life score (quality of life scale for patients with mild hepatic encephalopathy).

Note: Screening results are valid within 7 days for clinical laboratory tests

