### **Diagnosis and main criteria for inclusion**

Each subject was required to meet all of the following criteria to be eligible for study enrollment:

- 1) 18-65 (inclusive) years of age, male or female.
- 2) Clinically diagnosed with liver cirrhosis.
- 3) Fasting venous blood ammonia above upper limit of normal (ULN).
- 4) Organ functions must meet the following criteria:
  - a) Peripheral blood: absolute neutrophil count  $\geq 0.5 \times 10^9/L$ , platelet  $\geq 20 \times 10^9/L$ , hemoglobin  $\geq 8$  g/dL.
  - b) Liver: aspartate aminotransferase (AST) and alanine aminotransferase (ALT)  $\leq 5 \times$  ULN; serum total bilirubin (TBL)  $\leq 5 \times$  ULN.
  - c) Kidney: creatinine clearance  $\geq 60$  mL/min.
  - d) No malabsorption or other gastrointestinal disorders that affect drug absorption.
- 5) Weight  $\geq 45$  kg and body mass index [BMI = weight (kg)/height (m^2) ] between 18 and 34 (inclusive) kg/m^2.
- 6) Subjects (including their partners) will have no pregnancy plan and voluntarily take effective contraceptive measures within 6 months after drug withdrawal. Refer to Appendix 9 for specific contraceptive measures.

- 7) Subjects or their legal representatives sign the Informed Consent Form and fully understand the content, procedures, and potential adverse reactions prior to the initiation of the study.
- 8) Able to complete the study per the requirements in the study protocol.

Subjects meeting any of the following criteria were ineligible for study enrollment:

- 1) Subjects who are allergic to rifamycin or quinolone antibacterial agents or those with an allergic constitution.
- 2) Pregnant or lactating women, or women of childbearing age with a positive pregnancy test from the screening period to initiation of the study treatment.
- 3) Subjects with serious nervous or mental disorders.
- 4) Subjects with Child-Pugh class C liver cirrhosis.
- 5) Subjects with Grade 2 or above hepatic encephalopathy.
- 6) Subjects who have been diagnosed with *Clostridium difficile*-induced pseudomembranous enteritis within 3 months.
- 7) Subjects who have had systemic infection or gastrointestinal bleeding within 7 days prior to screening.
- 8) Subjects with clinically significant abnormal clinical laboratory tests or other clinical findings indicative of clinically significant disorders that, in the opinion of the investigator, make them not eligible for this clinical study.

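### The percent-normal ammonia comparison names no baseline term, which leaves chance imbalance in starting ammonia uncorrected and costs power in very small arms

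*Combined protocol and SAP*

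**What the plan says.** Inclusion criterion 3 asks for "Fasting venous blood ammonia above upper limit of normal (ULN"), with no margin above the limit and no repeat value. The Admission (Baseline) Evaluations section lists "fasting blood ammonia concentration, asterixis" and other assessments for D-1, so a baseline ammonia value is collected. It does not say that this value must still be above ULN.

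Under Efficacy analysis, "Normal fasting venous blood ammonia concentrations across all post-baseline visits in each dose group and the placebo group will be counted". The denominator is measurements rather than patients, since "their percentages in all measurements will be calculated". The comparison is then stated in one clause: "Logistic regression will be used to compare the difference in the percentage of normal blood ammonia concentrations between each dose group and the placebo group". No covariate is named, and nothing is said about several values coming from the same patient. Normal is not defined separately; at or below ULN is the natural reading.

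Two other between-group models in that section do name baseline. For asterixis the model names both terms: "Logistic regression (with baseline and group as". For quality of life it is an analysis of covariance with baseline as covariate and group as factor.

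Ammonia is also analysed on its continuous scale. For change from baseline, "analysis of covariance will be performed for differences between treatment groups and between each treatment group and the control group" (rank tests if the data are not normal). In addition, "The areas under the blood ammonia concentration-time curve will be calculated" and compared by t-test or rank sum test.

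**The concern.** Patients are selected for being above a limit and are later scored on whether they are at or below it. A patient who starts just above ULN will often cross on visit-to-visit variation alone; a patient who starts at twice ULN rarely will. Starting position is therefore a strong predictor of this outcome.

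Randomization balances starting position only on average. With 8 patients on a dose, and 4 or at most 12 on placebo, a difference of two patients in who starts near the limit is an ordinary chance event, and an unadjusted contrast carries it in full. At stake are the precision and power of this comparison, and how a raw percent-normal figure for a dose group is read.

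**Working it through.** **Inputs from the documents.** Each dose group has 12 patients at 2:1 (Study Design): 12 × 2/3 = 8 active and 12 × 1/3 = 4 placebo. Over three dose groups, placebo is 3 × 4 = 12 if pooled. Efficacy is a secondary, preliminary objective. No alpha, power, effect size, ammonia variability, expected normal rate or ammonia visit list is given, so there is no planned figure to reproduce. Everything below rests on assumed values.

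**Step 1: dependence on starting position.** Let m be the log of a patient's own mean ammonia relative to ULN, and s the visit-to-visit SD on the log scale. With no drug effect, P(normal) = Φ(−m/s). Take s = 0.25.
- Mean at 1.05 × ULN: m = ln 1.05 = 0.049, and Φ(−0.195) = 0.42.
- Mean at 2 × ULN: m = ln 2 = 0.693, and Φ(−2.77) = 0.003.

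**Step 2: the same after selection at entry.** Simulation assumptions: between-patient log SD 0.30; visit SD 0.15, 0.25 or 0.35; source median 1.0, 1.3 or 1.7 × ULN; entry on one screening value above ULN; 200,000 patients per setting. With no drug effect, 3% to 36% of post-baseline values are normal, and the same share is already normal on D-1. Among patients screened below 1.2 × ULN the rate is 18% to 46%; among those above 1.5 × ULN it is 0.3% to 26%.

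**Step 3: what an imbalance does.** In the middle setting (median 1.3, SD 0.25) those two rates are 30.1% and 6.8%, a gap of 23.3 points. If two patients start near the limit instead of far above it, the arm's expected percentage moves by:
- 8 patients: 2/8 × 23.3 = 5.8 points
- 4 patients: 2/4 × 23.3 = 11.7 points
- 12 patients: 2/12 × 23.3 = 3.9 points

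A separate simulation (between-patient SD 0.40, visit SD 0.15 to 0.35, source mean of the log ratio 0 to 0.5, 4 visits) put the chance SD of the unadjusted 8 versus 12 contrast, with no drug effect, at 6 to 14 percentage points.

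**Step 4: power with and without D-1 ammonia.** Outcome: each patient's proportion of normal values, analysed by linear model. Step 2 assumptions, 4 post-baseline values, 30% fall in ammonia, two-sided 0.05, 800 trials per setting (Monte Carlo SE at most about 1.8 points).

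| Source median (× ULN) | Visit SD | 8 vs 12: without → with | 8 vs 4: without → with |
|---|---|---|---|
| 1.0 | 0.15 | 88.5% → 97.6% | 62.4% → 79.9% |
| 1.0 | 0.35 | 58.4% → 63.0% | 35.1% → 37.6% |
| 1.3 | 0.15 | 79.2% → 92.5% | 36.0% → 58.0% |
| 1.3 | 0.35 | 54.8% → 60.4% | 26.4% → 28.2% |
| 1.7 | 0.15 | 52.0% → 62.4% | 4.2% → 19.0% |
| 1.7 | 0.35 | 45.9% → 50.4% | 17.6% → 18.0% |

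The gain is 4.5 to 13.3 points at 8 versus 12, and 0.4 to 22 points at 8 versus 4. Type I error at 8 versus 12 was 0.6% to 5.8% without the D-1 value and 1.5% to 5.6% with it.

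Other assumptions, also at 8 versus 12, agree in direction:
- Between-patient SD 0.40, visit SD 0.25, mean log ratio 0.3. For a 26% fall, 33% → 37% with 2 visits and 42% → 58% with 6. For a 39% fall, 69% → 80% and 82% → 95%. Gains are 4 to 16 points.
- The separate simulation of step 3, with a 30% fall: gains of 6 to 18 points (5 to 25 at 8 versus 4).
- A further set with other assumed SDs and visit counts: gains of about 5 to 24 points, with type I error at or below about 6%.

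**Step 5: the unit of analysis.** If every measurement is treated as independent, which the wording allows, the false-positive rate in the step 2 settings is 9% to 23%. Adding D-1 ammonia to such a measurement-level logistic model does not cure this: with 6 visits, type I error was still about 10% to 17%. A quasi-binomial version on patient proportions ran at 7% to 10%. With 2 visits and visit SD 0.15, the covariate raised separated or non-estimable logistic fits from 46% to 53% under no effect.

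**The case against.** The trial is randomized and placebo-controlled, so chance normal values arise in both arms and do not favour either. Ammonia is also compared by analysis of covariance and by AUC, efficacy is secondary and preliminary, and silence about covariates is not a decision to exclude them. Adding a baseline term to a logistic regression of all measurements would leave false positives well above 5% and would not always gain power. All sizes are assumed.

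Most of this stands. It limits the consequence to variance and power, and it shapes the remedy. It does not remove the point: the section names baseline for two other models and not here, and the value is already collected. The companion analyses help only in part. The covariance analysis does not list its covariates, its rank-test fallback and the AUC comparison name no baseline term, and neither answers the return-to-normal question.

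A reader might go further and infer that noise near ULN hides the drug effect. The checks do not support that. Under a 30% fall, percent normal rises from 21% to 72% (median 1.0, visit SD 0.15) and from 36% to 68% (median 1.0, visit SD 0.35). At visit SD 0.15 and 8 versus 12, unadjusted power is higher when patients sit near the limit (89% at median 1.0, 52% at 1.7).

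A reader might also infer that the plan needs a confirmation or minimum-change rule. Requiring a 20% fall as well changes power by only about −1 to +9 points at 8 versus 12, and a confirmed-normal count lost power as the main measure. Defining normal by ULN is simply what the word means.

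**Conclusion.** The point holds as a gap in the analysis of one secondary comparison. With no baseline term, chance imbalance in starting ammonia goes uncorrected and power is lost. Over the assumptions tried, a patient-level model with D-1 ammonia gains roughly 4 to 24 points at 8 versus 12, with type I error no higher than about 6%. At 8 versus 4 the gain runs from almost nothing to about 25 points. The harm is added variance, not systematic bias, and the continuous ammonia analyses limit it.

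These figures rest on assumed SDs, source levels, visit counts and effect sizes, on at or below ULN as the meaning of normal, and on linear models for patient proportions. Only direction and rough size should be relied on. The gain does not carry over to a logistic regression that treats all measurements as independent.

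**What to change.** In the Efficacy analysis section, restate the percent-normal comparison as follows.
- Define normal explicitly, and name group and log D-1 fasting ammonia as the independent variables.
- Use either one value per patient (the proportion of post-baseline values that are normal) or a model that accounts for repeated values within a patient, with a small-sample correction. If a logistic model is kept and separates, use a penalised fit. Do not treat all measurements as independent.
- Report the baseline-adjusted contrast with its 95% CI. Show each dose group's raw percentage only beside the placebo percentage, which indicates how often normal values occur without drug.
- State whether placebo is pooled over the three dose groups.

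No new data, visits or patients are needed, and eligibility is unchanged. The cost is one model degree of freedom and slightly more analysis work.

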**Pharmacokinetics Sample Collection Time Point:**

- Day 1: 30-60 min prior to the first dose, and 0.5 h, 1 h, 2 h, 3 h, 4 h, 5 h, 6 h, 8 h, 10 h and 12 h post-dose (prior to the next dose).
- Days 3, 5, 7, 9, 11 and 13: 30-60 min prior to the first dose.
- Day 15: 30-60 min pre-dose, and 0.5 h, 1 h, 2 h, 3 h, 4 h, 5 h, 6 h, 8 h, 10 h, 12 h, 24 h and 36 h post-dose.

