For HE grades, Wilcoxon signed rank test will be used to determine whether changes from baseline in each treatment group are different on D7 or D15. Wilcoxon rank sum test will be used to determine whether changes on D7 and D15 are different between treatment groups and between each treatment group and the control group.

If D7 or D15 data are missing, the last observation carried forward (LOCF) approach will be used for imputation.

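### The between-arm NCT-A/DST comparison is set for D7 and D5 where every other rule that names days uses D7 and D15; adjusting for the D-1 score in the same edit is an optional gain, not the repair of an error

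*Combined protocol and SAP*

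**What the plan says.** All the rules below stand in the Efficacy analysis section under Statistical methods, unless another section is named.

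- **NCT-A and DST, between arms:** "Inter-group t-test or Wilcoxon rank sum test will be used to determine whether changes on D7 and D5 are different", both among the treatment groups and against control.
- **NCT-A and DST, within arm (the sentence just before):** the test is to "determine whether the change from baseline in each treatment group is 0 on D7 or D15".
- **Asterixis, between arms:** logistic regression, or "non-parametric methods will be used for inter-group comparison of D7 and D15 results". The within-arm asterixis rule also uses baseline, D7 and D15.
- **HE grade, between arms:** "Wilcoxon rank sum test will be used to determine whether changes on D7 and D15 are different between treatment groups". The within-arm HE rule uses the same two days.
- **Missing data:** "If D7 or D15 data are missing", the last observation is carried forward.
- **Quality of life, between arms:** "analysis of covariance (baseline as the covariate and group as the fixed factor"), to see whether "changes from baseline at each post-baseline visit are different between the groups (including the placebo group").

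The ammonia and quality-of-life rules name no days; they refer to every post-baseline time point or visit. The Pharmacokinetics section lists Day 5 as a sampling day: "Days 3, 5, 7, 9, 11 and 13: 30-60 min prior to the first dose". Under Admission (Baseline) Evaluations, NCT-A and DST are measured on D-1. Study Design gives 8 active and 4 placebo patients in each of three sequentially enrolled dose groups.

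**The concern.** NCT-A and DST are the neuropsychological indicators named in the second secondary objective. The sentence with D5 is the only one that specifies their comparison between arms. Followed to the letter, it calls for a test on a day for which the text names no neuropsychological assessment, and it leaves the comparison with placebo at the end of treatment without a specified test.

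The same sentence raises a question of efficiency. It compares changes by a t-test or a rank sum test, so the D-1 score enters only by subtraction. With 8 active patients per dose, some precision may be left unused, and the plan already adjusts for baseline in the quality-of-life analysis.

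**Working it through.** **(a) The days.** Efficacy rules that name days:

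| Rule | Days |
|---|---|
| NCT-A/DST, within arm | D7, D15 |
| **NCT-A/DST, between arms** | **D7, D5** |
| Asterixis, within arm | baseline, D7, D15 |
| Asterixis, between arms | D7, D15 |
| HE grade, within arm | D7, D15 |
| HE grade, between arms | D7, D15 |
| LOCF | D7, D15 |

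Six of the six other rules agree. The between-arm HE sentence is worded almost identically and reads D15. Outside the quoted sentence, Day 5 occurs only as a PK sampling day. The supplied text has no visit schedule to check against.

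**(b) The covariate.** The plan gives no power, SD, alpha or correlation for these scores, so there is no figure to reproduce.

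*From the document:* 12 × 2/3 = 8 active and 4 placebo patients per dose group; 3 × 8 = 24 active and 3 × 4 = 12 placebo; 36 in all.

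*Assumed:* two-sided 5%; a true difference of 1 SD of the score; equal SDs; correlation r between the D-1 and the later score; placebo pooled to 12; no cohort effect.

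Variance of the dose-minus-placebo estimate, in SD² units, with k = 1/8 + 1/12 = 0.2083:

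- t-test on change, df 18: 2(1 − r)k
- ANCOVA on the two arms compared (N = 20), df 17: (1 − r²)k × [1 + 1/(20 − 2 − 2)] = (1 − r²)k × 1.0625
- ANCOVA on all four arms (N = 36), df 31: (1 − r²)k × [1 + 1/(36 − 4 − 2)] = (1 − r²)k × 1.0333

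At r = 0.5 the three variances are 0.2083, 0.1660 and 0.1615. The standard errors are 0.456, 0.407 and 0.402, and the noncentrality values (1/SE) are 2.19, 2.45 and 2.49. Power from the noncentral t distribution:

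| r | t-test on change | Two-arm ANCOVA | All-arm ANCOVA |
|---|---|---|---|
| 0.5 | 54.5% | 63.8% | 67.4% |
| 0.7 | 76.3% | 80.1% | 83.2% |
| 0.8 | 90.6% | 91.6% | 93.6% |
| 0.9 | 99.6% | 99.6% | 99.8% |

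The variance ratio of ANCOVA to t-test is (1 + r)/2 times 1.0625 (two arms) or 1.0333 (all arms). It reaches 1 at r = 2/1.0625 − 1 = 0.88 and r = 2/1.0333 − 1 = 0.94 respectively.

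**Is the all-arm model's extra power safe?** It borrows residual variance from the two doses not being compared. Simulation with the residual SD of those two arms changed:

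- Half as large: type I error of the all-arm ANCOVA is about 10.5 to 11%. The t-test and the two-arm ANCOVA stay at 5%.
- 1.5 times as large: power of the all-arm ANCOVA falls below that of the t-test, at about 49% v 55% (r = 0.5), 68% v 76% (0.7) and 84% v 91% (0.8).

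**Is an all-arm rank version safe?** With skewed (lognormal) scores, the tested dose inactive and the other two doses shifted by 1 and 2 SD, ANCOVA on ranks taken across all arms has type I error of about 7 to 8% for r from 0.5 to 0.8. Ranking within the two arms compared keeps it at about 5%.

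**The case against.** **The day is an obvious slip.** The preceding sentence sets D7 and D15 for the same scores, the LOCF rule covers D15, and a D5 test could not be run if nothing was measured then. Changes at every post-baseline visit are summarised anyway. A character lost in reading the PDF cannot be fully excluded, although the neighbouring D15s survived. All this stands and keeps the point minor. It does not remove it: a summary is not a between-arm test, and an operative rule should be corrected in the text rather than interpreted at analysis.

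**The covariate is a preference.** Efficacy is secondary and preliminary, and every power figure rests on assumed values. HE grade, ammonia AUC and the non-normal ammonia fallback are also unadjusted, and the ammonia ANCOVA names no covariate. This stands too, so (b) can only be offered as an improvement.

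**Stronger readings that the documents do not support.**

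- A reader might infer that the D15 comparison was deliberately dropped or that D5 was in fact analysed. Nothing in the text says so.
- A reader might infer that a test on unadjusted change is biased for want of the covariate. It is not: the covariate buys precision only.
- A reader might infer that one model over all arms, with an all-arm rank version as fallback, is a gain without loss. The simulations above show that it is not.

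**Pooled placebo.** The wording implies a single control group but states no pooling rule. Because dose groups enrol in sequence, 8 of the 12 pooled placebo patients were not randomised alongside any given dose. The t-test and the ANCOVA share this limit; a smaller standard error does not remove bias from drift between cohorts.

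**Conclusion.** (a) holds as an internal inconsistency of minor weight: one of two days is wrong in one rule, for two endpoints. It needs no assumption beyond the text as supplied.

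(b) holds as an optional improvement for normally distributed scores. On the two arms compared, the gain is about 9 points of power at r = 0.5, 4 at 0.7, 1 at 0.8 and none at 0.9. That rests on the assumed alpha, effect size, equal SDs, pooled placebo and absence of a cohort effect. The larger all-arm gain (to about 67 to 68%, 83% and 93 to 94% at r = 0.5, 0.7 and 0.8) also requires equal residual variance in all arms, which cannot be relied on here. If placebo were instead kept by cohort and separate 8 v 4 models fitted, the covariate would cost a little power at high correlation (64.5% to 63.5% at r = 0.8; 90.8% to 88.1% at r = 0.9).

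**What to change.** 1. In the between-arm NCT-A/DST sentence, replace D5 by D15. Parts of the synopsis are in the past tense, so if the analysis has already been run, confirm which day was tested and record the correction.
2. Optionally, for normally distributed scores, replace the between-arm t-test by an ANCOVA of the change in the age-corrected score at D7 and at D15, with group as fixed factor and the D-1 score as covariate. Fit it to the two arms compared, or fit all arms with group-specific variances.
3. Keep the planned rank sum test for non-normal data, or rank within the two arms compared only. Do not rank across all arms.
4. State that placebo is pooled over the sequentially enrolled dose groups and is therefore partly non-concurrent.

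Cost: item 1 is a one-character correction. Item 2 needs no new data, but uses one degree of freedom (17 instead of 18), assumes a common slope, and brings little or nothing at r of about 0.9 or more. If results are already known, item 2 is a change of method and not of wording, and should be labelled post hoc.
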